3.3 SCREEN FAILURES

Screen failures are defined as subjects who consent to participate in the clinical study but are not subsequently entered in the study. A minimal set of screen failure information is required to ensure transparent reporting of screen failure subjects to meet the Consolidated Standards of Reporting Trials (CONSORT) publishing requirements and to respond to queries from regulatory authorities. Minimal information includes demography, screen failure details, eligibility criteria, and any SAE.

For individuals who do not meet the criteria for participation in this study (screen failure) and for whom resolution of the screen failure reason may not be expected within a reasonable time frame, the screen failure will be performed. The subject may be rescreened; if their clinical condition

changes, subject numbers will not be reused and a new subject number will be assigned. All the screening procedures will be repeated and entered in the screening visit pages.

In case the subject is a temporary screen failure, there is no need to have subject re-consent (eg, new ICF signed) if the subject finally participates in the trial. However, if the reason for temporary screen failure is a reason that might have altered the initial given agreement of the subject to participate, the Investigator should ensure the willingness of the subject to continue or redo some screening procedures and his/her participation to the trial. This oral agreement should be documented in the subject's chart. All the tests out of protocol window should be repeated and entered to the additional pages.

3.3.1 Withdrawal, removal, and replacement of subjects

All subjects will be informed that they have the right to discontinue study drug or to withdraw from the study at any time, for any reason, without prejudice, and without having to justify their reasons or decisions. Additionally, the Investigator may discontinue a subject's study drug at any time if he/she considers that to be in the subject's best interest or if the Investigator determines that continuing study drug would result in a significant safety risk for the subject.

A discontinuation of study drug occurs when an enrolled subject ceases study drug, regardless of the circumstances, prior to completion of the study. However, every effort should be made to observe subjects who have been dosed until the scheduled end of the follow-up period, even if they prematurely discontinue study drug.

Withdrawal of consent for intervention should be distinguished from withdrawal of consent for follow-up visits and from withdrawal of consent for non-subject contact follow-up, eg, medical record checks. The site should document any case of withdrawal of consent.

If subjects no longer wish to take the IMP, they will be encouraged to remain in the study. The Investigators should discuss with them key visits to attend. The value of all their study data collected during their continued involvement will be emphasized as important to the public health value of the study. Subjects who withdraw from the study intervention should be explicitly asked about the contribution of possible AEs to their decision, and any AE information elicited must be documented. All study withdrawals should be recorded by the Investigator in the appropriate screens of the eCRF and in the subject's medical records. In the medical record, at least the date of the withdrawal and the reason should be documented.

In case of premature discontinuation of study drug, the Investigator should schedule an early termination visit to record AE data and to collect samples for laboratory evaluations. This visit should be documented in the appropriate eCRF. The Investigator will record the reason for the study drug discontinuation, provide or arrange for appropriate follow-up for such subjects, and document the course of the subject's condition. In addition, the Investigator will report the subject's study drug discontinuation or study withdrawal to the Sponsor immediately.

Valid reasons for a subject to discontinue the study drug or to withdraw from this clinical study include but are not limited to:

- Withdrawal of informed consent

- Subject's decision to discontinue study drug
- Reaching the treatment stopping rules. Please see [Section 3.3.1.1](#) below
- Occurrence of AEs for which permanent discontinuation is considered necessary by the Investigator
- Investigator's decision (eg, if in the Investigator's opinion it is not in the best medical interest of the subject to continue participation in the study)
- Any protocol deviation that may result in a significant risk to the subject's safety or protocol deviations that will interfere with the efficacy endpoints of this study
- Lost to follow-up (the subject stopped coming for visits, and study personnel are unable to contact the subject)

3.3.1.1 Individual treatment stopping criteria

Any Grade 2 AE (except for renal function parameters related to the underlying disease process including eGFR, creatinine, BUN, and urinalysis) not resolved prior to the administering the next dose and deemed by the Investigator to be at least "possibly related" to study drug would result in a pausing of dosing (eg, dose not given) until the AE improves to \leq Grade 1. Injection site reactions will be graded according to [Table 6](#). Any Grade 2 (except erythema/redness) or Grade 3 ISRs which had not resolved or reached Grade 1 ("Mild", eg, limited tenderness, and/or induration, except erythema/redness) prior to the next dose, would result in a pausing of dosing. The continuation of dosing and dose level would be decided upon review between the Investigator and the Genzyme Corporation Study Medical Manager. For further details in dose reduction, see [Section 4.5](#).

Occurrence of any Grade 3 (Severe) or higher AE (except for ISRs and renal function parameters related to the underlying disease process including eGFR, creatinine, BUN, and urinalysis) will result in the cessation of dosing of the subject, unless it can be shown that the event was unrelated to participation in the clinical trial. The DMC will review the circumstances of the AE with the Sponsor and unblind the subject, as appropriate, to evaluate potential relatedness to study drug and will make a recommendation regarding the further dosing of the subject to the Sponsor. After deliberations, DMC will provide guidance to the Sponsor who will implement recommendations and communicate to the site.

With regard to AEs, study drug should be discontinued for subjects who experience any of the following:

- Grade 3 thrombocytopenia (platelet count from $<50\,000$ to $25\,000/\text{microL}$) will trigger cessation of dosing for the subject.
- ALT or AST $>5 \times$ ULN, or ALT or AST $>3 \times$ ULN in association with total bilirubin $>2 \times$ ULN.
- An unintended weight loss of $\geq 20\%$ from baseline.

- $\geq 50\%$ decline for eGFR from the last measurement or confirmed ESRD (eGFR ≤ 15 mL/min/1.73 m² or dialysis or renal transplantation is needed).

In case of worsening of eGFR (that do not reach stopping criteria) or UPCR, the Investigator or the Sponsor could repeat the test before the next scheduled one as often as medically needed. The Sponsor needs to be consulted before a decision to discontinue the patient, unless it is a case of emergency.

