1.3 RISKS AND BENEFITS

1.3.1 Potential and identified risks

Based on a comprehensive review of available data for the lademirsen clinical development program, thrombocytopenia and ISRs are considered as important identified risks; and nephrotoxicity based on non-clinical histologic findings in the glomerulus, hepatotoxicity, clinically meaningful immunogenicity, and embryo-fetal toxicity are considered as important potential risks.

For additional information on lademirsen (SAR339375) risks and benefits, refer to the Investigator's Brochure.

For study conduct in Germany, please see [Section 10.5.1.1](#) for further details.

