3.4 DISCONTINUATION OF THE STUDY

The Sponsor may terminate the study at any time for any reason. In the event the study is terminated, the Institutional Review Board (IRB)/Ethics Committee (EC) and Competent Authority will be notified of the decision.

Study Suspension and Stopping Criteria

The occurrence of two similar Grade 3 (or higher) AEs (except for ISRs and renal function parameters related to the underlying disease process including eGFR, creatinine, BUN, and urinalysis), or any death or two unexpected SAEs considered at least possibly related to participation in the clinical trial, or any TEAE that in the opinion of the Sponsor is of potential clinical significance for subjects safety will result in the recommendation to suspend all dosing and stop recruitment, then will trigger an ad hoc meeting with the DMC who will be asked to

consider the appropriateness of study conduct continuation unchanged, early study termination or modification.

Upon suspension of dosing, a full, unblinded review of the AEs will be performed by the DMC to evaluate the AEs and potential relationship to exposure to the study drug. Following the full, unblinded safety review, one of three outcomes is possible:

1. The study may be terminated.
2. The study design may be amended. For example, the dose of study drug may be reduced for all subjects (to 110 mg SC every other week (the pre-specified dose reduction for a Grade 2 AE), the dose regimen may be changed to reduce the dosing frequency, or inclusion/exclusion criteria may be modified (eg, baseline platelet count or other relevant laboratory or clinical parameter).
3. Stopping criteria are at the discretion of the DMC, the study may continue as originally planned, based on clear evidence that the stopping criteria have not been met and measures are in place to ensure subject safety.

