4.5 DOSE REDUCTION

Before administering each dose of study drug, the Investigator or delegate will review a subject's most recent safety data. A subject's platelet count will be obtained weekly before dose administration. Platelet counts will be measured from a central laboratory and can exceptionally be measured from a local laboratory. The most recent subject's platelet counts, but not older than 10 days, will be reviewed by the Investigator/physician before drug administration. Following the resolution of a Grade 2 AE or increase in aminotransferases (return to normal or \leq Grade 1 for AE) that does not otherwise trigger a stopping rule (see [Section 3.4](#)), the Investigator in consultation with the Sponsor Medical Manager may reduce an individual subject's dose to 110 mg Q2W. Dose reductions should be discussed with the Sponsor Medical Manger before implementation.

Grade 2 thrombocytopenia (platelet count from <100 000 to 50 000/microL) will result in suspension of dosing pending a return of platelet count to > LLN and review by the Investigator and the Sponsor Medical Manager. If dosing is to resume, it will be reduced to 110 mg Q2W.

For actions related to laboratory abnormalities that are indicative of potential hepatotoxicity, any subject experiencing a moderate (Grade 2) alkaline phosphatase, or bilirubin elevation will have a dose suspension and related laboratory test should be done weekly until the value(s) return to the normal range. For actions related to elevation of aminotransferases, please refer to [Section 10.3.2](#). If dosing is to resume, it will be reduced to 110 mg Q2W.

Injection site reactions will be graded according to [Table 6](#). Any Grade 2 (except erythema/redness) or Grade 3 ISR must have resolved or reached Grade 1 (“Mild”, eg, limited tenderness, and/or induration, except erythema/redness) prior to the next dose or subsequent dosing will be suspended. Consideration of resumed dosing at dose 110 mg Q2W will be based on review of the AE and time course to resolution in consultation with the Sponsor Medical Manager.

Once a subject’s dose has been reduced, it will not be increased.

For a regional or national emergency declared by a governmental agency, contingency measures are included in [Section 10.6](#).

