10.2 APPENDIX 2: CLINICAL LABORATORY

The tests detailed in [Table 7](#) will be performed by the central laboratory.

- Local laboratory results are only required in the event that the central laboratory results are not available in time for either IMP administration and/or response evaluation. Additionally, if the local laboratory results are used to make either an IMP decision or response evaluation, the results and normal ranges must be entered into the CRF.

- Protocol-specific requirements for inclusion or exclusion of subjects are detailed in [Section 3.2.1](#) and [Section 3.2.2](#) of the protocol.
- Additional tests may be performed at any time during the study as determined necessary by the Investigator or required by local regulations.

Table 7 - Protocol required safety laboratory assessments

[figure not shown]
Laboratory assessments	Parameters
Hematology	To include hemoglobin, hematocrit, platelet count, total white blood cell (WBC) count with 5-part differential count, and total red blood cell count.
Clinical chemistry	To include creatinine, blood urea nitrogen, glucose, uric acid, total cholesterol, total protein, albumin, total and direct bilirubin, ALT, AST, alkaline phosphatase, GGT, lactate dehydrogenase, sodium, potassium, chloride, bicarbonate, calcium, iron, phosphate, total cholesterol, triglycerides, HDL, LDL, prothrombin time (PT), activated partial thromboplastin time (aPTT), international normalized ratio (INR), and fibrinogen.
Routine urinalysis	To include specific gravity, pH, glucose, ketones, blood, protein, nitrate, leukocyte esterase, urobilinogen, and bilirubin. If specific gravity, PH, glucose, ketones, nitrate, leukocyte esterase, urobilinogen, and bilirubin parameters on the dipstick are abnormal, the investigation will be done by the Investigator as per local practice.

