	In the list of adverse events for which study drug should be discontinued, the third bullet regarding unintended weight loss was revised to increase the threshold for change to $\geq 20\%$ from baseline. In addition, the fourth bullet regarding estimated glomerular filtration rate and its decline was revised to include a decline of $\geq 50\%$ from the last measurement, and not from baseline, or confirmed end-stage renal disease.	To reflect that 1) estimated glomerular filtration rate decrease is the expected progression of the underlying disease (as a reminder, change in estimated glomerular filtration rate is the primary efficacy endpoint of this study), and 2) mild or moderate weight loss is an expected manifestation of the underlying disease.
Protocol Synopsis / Study Suspension and Stopping Criteria AND 3.4 Discontinuation of the Study	The phrase "except for ISRs and renal function parameters related to the underlying disease process including eGFR, creatinine, BUN, and urinalysis" was added in parenthesis to the first paragraph.	To align with the revised guidance for study drug dosing with regard to injection site reactions or adverse events associated with renal function parameters.
Protocol Synopsis / Table 1	Schedule of events revised to include 1 day post injection follow-up assessments to be performed on a weekly basis.	For clarification.
	Serum chemistry, lipid panel, and high-sensitivity C-reactive protein assessments included for unscheduled visits.	For consistency with the assessments to be performed at unscheduled visits during the open-label treatment extension period and follow-up period.
Protocol Synopsis / Table 2	Schedule of events revised to (1) remove blood sampling for pharmacokinetic (pre-dose) assessments at unscheduled visits, and (2) include 1 day post injection follow-up assessments to be performed on a weekly basis from Week 48 to Week 96 (corresponding footnote [cc] added to describe purpose/scope of follow-up assessment).	Pharmacokinetic sampling at unscheduled visits removed for consistency with the assessments to be performed during the double-blind, placebo-controlled treatment period. Post injection follow-up assessments added for clarification.

Section # and Name	Description of Change	Brief Rationale
	Blood sampling for complement removed from unscheduled visits.	For consistency with the assessments to be performed at unscheduled visits during the double-blind, placebo-controlled treatment period.

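### The 50% limb of the eGFR stopping criterion is measured from the last measurement, so an unscheduled repeat can reset the reference and keep the limb from being met

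*Protocol*

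**What the plan says.** Protocol 3.3.1.1 lists four findings for which study drug should be discontinued; the synopsis repeats them. The fourth is a 50% or greater "decline for eGFR from the last measurement or confirmed ESRD". The other three have fixed references: an absolute platelet count, multiples of the upper limit of normal, and weight change from baseline.

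The paragraph after the list deals with repeat testing. "In case of worsening of eGFR (that do not reach stopping criteria) or UPCR", it says, "the Investigator or the Sponsor could repeat the test before the next scheduled one as often as medically needed". Footnote t to Table 1 gives the Investigator a similar permission for eGFR. Local results can also enter: Appendix 2 (Section 10.2) says "Local laboratory results are only required in the event that the central laboratory results are not available in time" for a dosing decision or response evaluation.

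Neither the Protocol nor the SAP says whether an unscheduled or local value replaces the reference. The amendment history (10.8.1) shows that the change of reference was intended: the limb was revised to run "from the last measurement, and not from baseline, or confirmed end-stage renal disease", because eGFR decline is expected in this disease. It does not define the new reference any further.

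**The concern.** The ordinary meaning of the last measurement is the one immediately before. An investigator who re-tests a worsening participant then splits one large fall into smaller steps, none of which need reach 50%. Closer monitoring makes the acute-fall limb harder to meet, which is the wrong direction for a safety rule.

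This matters because Protocol 1.3.1 names "nephrotoxicity based on non-clinical histologic findings in the glomerulus" as an important potential risk. Whether a stopping criterion is met should not depend on whether someone repeated the test.

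**Working it through.** **Inputs.** Threshold and reference: Protocol 3.3.1.1. Repeats: 3.3.1.1 and Table 1 footnote t. Scheduled eGFR at baseline, Week 2, Week 4 and every 4 weeks thereafter: SAP 5.3. Entry eGFR above 35 and below 90: Protocol 3.2.1. ESRD limb at 15 or below: 3.3.1.1. The plan gives no figure for how this rule performs, so there is none to reproduce.

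**Masking condition.** Let P be the previous scheduled value, R one unscheduled repeat and N the next scheduled value. Percent fall = 100 × (reference − new)/reference.

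- Scheduled to scheduled, the limb is met when N ≤ 0.5P.
- With the repeat counted, it is not met at R if R > 0.5P, and not met at N if N > 0.5R.
- The repeat therefore hides the event when 0.5P < R < 2N.

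| P / R / N | P to N | P to R | R to N | Masking window for R |
|---|---|---|---|---|
| 50 / 36 / 24 | 52% | 28% | 33% | 25 to 48 |
| 60 / 40 / 28 | 53.3% | 33.3% | 30.0% | 30 to 56 |
| 89 / 50 / 26 | 70.8% | 43.8% | 48.0% | 44.5 to 52 |

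The window exists only if N > 0.25P, so one repeat can hide a fall of just under 75%. Below P = 60 the ESRD limb binds first: at P = 36 the largest hidden fall is 1 − 15/36 = 58.3%. A repeat at or below half of P meets the limb itself (60 to 29 is 51.7%).

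The effect can also reverse. With 60 / 66 / 31, the literal reading gives 1 − 31/66 = 53% (met), while scheduled to scheduled gives 1 − 31/60 = 48% (not met).

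**How often.** The residual SD is redacted in Protocol 7.2.1, so this part rests on assumptions: residual SD 2 or 4; baselines 45, 60 and 80; an exponential fall; weekly repeats only while the latest value is at least 20% below baseline and the limb is not yet met; 200,000 simulated participants per cell. Random onset is uniform between two scheduled draws (Weeks 8 to 12).

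| Scenario | Limb met, literal | Limb met, repeats do not reset | Gap (points) |
|---|---|---|---|
| 60% over 4 weeks, onset at a scheduled draw | 85-100% | 88-100% | 0-3 |
| 60% over 4 weeks, random onset | 43-52% | 51-68% | 5-16 |
| 70% over 6 weeks, random onset | 39-67% | 77-89% | 22-39 |

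For the second row, a 10% repeat trigger gives a gap of 16-25 points and a 30% trigger gives 0-8. For the first row, a 10% trigger gives 0-14. Slower falls (60% over 6 weeks, 70% over 8 weeks) meet the limb under neither reading without noise.

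**False stops.** Under ordinary progression (mean decline 10 mL/min/1.73 m² per year, slope SD 4 or 8, entry eGFR 36, 45 or 60), false stops by Week 48 are at most 1.0% on the literal reading. They are at most 0.6% if only scheduled values serve as reference, and about 1% at most if the higher of the two references is used.

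**The case against.** The strongest answer is that the modelled harm is already visible elsewhere. Table 3 grades eGFR from the participant's own baseline: 30% or more is Grade 3, 50% or more is Grade 4. With baseline 60, a repeat of 36 is 1 − 36/60 = 40% down and already a Grade 3 AESI, reportable within 24 hours (9.1.1). In simulation, at least 99.98% of these acute falls produced a value at Grade 3 or worse. Unless exempt, such an event stops dosing under 3.3.1.1. Section 4.5 adds that "Before administering each dose of study drug, the Investigator or delegate will review" recent safety data. The Investigator may stop drug at any time (3.3.1). The Sponsor may recommend suspending dosing for "any TEAE that in the opinion of the Sponsor is of potential clinical significance for subjects safety" (3.4). The DMC monitors eGFR (6.2.17).

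Most of this stands, and it limits the consequence. It does not replace the limb. The Grade 3-or-higher rule exempts renal changes related to the underlying disease, and separating drug effect from disease is the hard judgement here. Grade 3 values are also common without toxicity: by Week 48 they appear in about half or more of simulated ordinary progressors entering at 36. AESI reporting is notification, and DMC consultation by the Investigator is optional.

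It is also fair to say that the simulated gaps depend on assumed inputs, and that a reference fixed only at the last scheduled value would lose the 60 / 66 / 31 stop and could go stale after a missed visit. The wording proposed below is built to avoid both.

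**Conclusion.** The point holds for one limb of one criterion, and it is modest. Followed as written, a repeat lying between half the previous scheduled value and twice the next value keeps the 50% limb from being met in a participant who loses half or more of eGFR between scheduled draws. The arithmetic needs no assumptions. The frequency does: gaps run from about 0-3 to about 22-39 percentage points depending on the assumed SD, repeat trigger, onset and shape of the fall.

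Three stronger readings are not supported. A reader might infer that acute renal injury would go unnoticed; the baseline-anchored grades and the other safeguards above say otherwise. A reader might infer that leaving baseline was a mistake; 10.8.1 records it as deliberate, with a reason. A reader might infer that a mandatory review at a 50% fall from baseline is missing and should be added. The DMC charter is a separate document and was not available, so its absence cannot be established. Such a review would also partly restore the anchor that Amendment 11 removed. In simulation it would send up to about half of those entering at eGFR 36 to ad hoc review by Week 96, largely for expected progression.

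**What to change.** In the synopsis and in 3.3.1.1, reword the fourth bullet along these lines:

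*A fall in eGFR of 50% or more from the last scheduled value (or the unscheduled value that replaced a missed scheduled one) or from the immediately preceding measurement, whichever is higher; or confirmed ESRD, defined as at present. Any later value, scheduled or unscheduled, may meet this criterion.*

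The new reference is never lower than the immediately preceding value, so every stop under the literal text remains, including 60 / 66 / 31 (reference 66, fall 53%). For 50 / 36 / 24 the reference is 50, the fall is 52% and the limb is met. Naming the replacement for a missed draw avoids a stale reference.

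The cost is one bullet in two places, with no new visits or samples. The downside is a very small number of additional stops, with false stops by Week 48 still at or below about 1%. Slow falls remain outside this limb: even when repeats do not reset the reference, without noise and with random onset it is met in only 49% of 60% falls over 4 weeks and 77% of 70% falls over 6 weeks. Table 3, the AESI rules and the ESRD limb stay unchanged, and no baseline-anchored mandatory review is proposed.
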